12.3.1 Serious Adverse Events

Table 12.3.1.1 Treatment-related* SAEs. Worst grade by patient

	Preferred Term	Grade 1		...	Grade 4		All**	
		N	%		N	%	N	%
SOC	Anemia NOS	X	X.X		X	X.X	X	X.X
Blood and lymphatic system disorders	...							
Cardiac disorders	Arrhythmia NOS							
	...							

(* or Unknown relationship (** Any grade

Table 12.3.1.2 Treatment-related* SAEs. Worst grade by cycle

	Preferred Term	Grade 1		...	Grade 4		All**	
		N	%		N	%	N	%
SOC	Anemia NOS	X	X.X		X	X.X	X	X.X
Blood and lymphatic system disorders	...							
Cardiac disorders	Arrhythmia NOS							
	...							

(* or Unknown relationship (** Any grade

Table 12.3.1.3 SAEs regardless of relationship. Worst grade by patient

	Preferred Term	Grade 1		...	Grade 4		All*	
		N	%		N	%	N	%
SOC	Anemia NOS	X	X.X		X	X.X	X	X.X
Blood and lymphatic system disorders	...							
Cardiac disorders	Arrhythmia NOS							
	...							

(* Any grade

Table 12.3.1.4 SAEs regardless of relationship. Worst grade by cycle

	Preferred Term	Grade 1		...	Grade 4		All*	
		N	%		N	%	N	%
SOC	Anemia NOS	X	X.X		X	X.X	X	X.X
Blood and lymphatic system disorders	...							
Cardiac disorders	Arrhythmia NOS							
	...							

(* Any grade

Listing 12.3.1.5 SAEs

Patient id.	Cycle	Preferred term code	Adverse event reported (verbatim)	Status	Grade	Relationship	Onset date	Resolved date	Action	Serious Criteria

SAEs narratives will be provided by the pharmacovigilance department.

12.3.2 Deaths

Table 12.3.2.1 Cause of death

Reason*	N	%
Malignant disease	X	X.X
Treatment-related adverse event		
Other		
Total		

(*) Denominator=Number of patients who died

Listing 12.3.2.2 Deaths

Patient id.	Death date	Cause	Comments	Autopsy	Autopsy report available	Number of cycles administered	Last infusion date	Time on treatment*	Time from Last dose**

(*)Time on treatment: defined as last infusion date plus 30 days, or date of death or subsequent therapy (whichever comes first) minus first infusion date. (**)Time from last dose defined as death date minus last infusion date.

Listing 12.3.2.3 Deaths due to AEs

Patient id.	Cycle	Preferred term code	Adverse event reported (verbatim)	Grade	Relationship	Onset date	Resolved date	Action

12.4 Clinical laboratory evaluation

12.4.1 Hematological abnormalities

Hematological toxicities classified according to the NCI-CTCAE will be calculated for all cycles. The worst grade reached by each patient during treatment will be also calculated.

If serious toxicities happen, special follow-up, with descriptives and graphs (boxplots, line plots) will be made to find out the pattern of thrombocytopenia and neutropenia within and between the different cycles.

Table 12.4.1.1 Hematological abnormalities during treatment, worst grade per patient

	N	Grade 1		...	Grade 4		All*	
		N	%		N	%	N	%
Leukopenia	X	X	X.X		X	X.X	X	X.X
Anemia								
Thrombocytopenia								
Neutropenia								
Lymphopenia								

(*) Any grade

Table 12.4.1.2 Hematological abnormalities during treatment, worst grade per cycle

	N	Grade 1		...	Grade 4		All*	
	N	N	%	...	N	%	N	%
Leukopenia	X	X	X.X		X	X.X	X	X.X
Anemia								
Thrombocytopenia								
Neutropenia								
Lymphopenia								

(*) Any grade

Listing 12.4.1.3 Grade 3-4 hematological abnormalities during treatment. Worst grade per patient

Patient id.	Test	Grade

Listing 12.4.1.4 Grade 3-4 hematological abnormalities during treatment. Worst grade per cycle

Patient id.	Test	Grade

Listing 12.4.1.5 Hematological tests not assessed at any treatment visit per patient

Patient id.	Lab. test

Listing 12.4.1.6 Hematological tests not assessed by patient and cycle

Patient id.	Cycle	Lab. test

Table 12.4.1.7 Platelets and RBC transfusions during the study

		Platelets (Units)		Red Blood Cells (Units)	
		N	(%)	N	(%)
Platelets (Units)	0 transfusions	X	X.X	X	X.X
	1 transfusion				
	...				
	Median (range)				
Red Blood Cells (Units)	0 transfusions				
	1 transfusion				
	...				
	Median (range)				

These tables will be complemented with plots for the median nadir of neutrophils (Figure 12.4.1.8), platelets count (Figure 12.4.1.9) and hemoglobin values (Figure 12.4.1.10) by cycle along the treatment. Furthermore, if appropriate, graphs of the intercycle time course of neutropenia and thrombocytopenia will be provided. Eventually, graphs comparing the time course during the first and second cycle will be created.

12.4.2 Biochemical abnormalities

Grades of liver toxicity and intercycle pattern of creatinine, CPK, bilirubin, transaminases increase and alkaline phosphatase increase during a cycle will be calculated, as it is explained in the corresponding section for hematological toxicities.

Table 12.4.2.1 Biochemical abnormalities during treatment, worst grade per patient

	N	Grade 1		...	Grade 4		All*	
	N	N	%	...	N	%	N	%
AST increase	X	X	X.X		X	X.X	X	X.X
ALT increase								
Total bilirubin increase								
ALP increase								
Creatinine increase								
CPK increase								

(*) Any grade

Table 12.4.2.2 Biochemical abnormalities during treatment, worst grade per cycle

	N	Grade 1		...	Grade 4		All*	
	N	N	%	...	N	%	N	%
AST increase	X	X	X.X		X	X.X	X	X.X
ALT increase								
Total bilirubin increase								
ALP increase								
Creatinine increase								
CPK increase								

(*) Any grade

Listing 12.4.2.3 Grade 3-4 biochemical abnormalities during treatment. Worst grade per patient

Patient id.	Test	Grade

Listing 12.4.2.4 Grade 3-4 biochemical abnormalities during treatment. Worst grade per cycle

Patient id.	Cycle	Test	Grade

Listing 12.4.2.5 Biochemical tests not assessed at any treatment visit by patient

Patient id.	Lab. test

Listing 12.4.2.6 Biochemical tests not assessed by patient and cycle

Patient id.	Cycle	Lab. test

These tables will be complemented with plots for the median peak of ALT (Figure 12.4.2.7), AST (Figure 12.4.2.8) and CPK values (Figure 12.4.2.9) by cycle along the treatment. If appropriate, graphs of the intercycle time course of ALT, AST and CPK will be provided.

12.4.3 Other metabolic parameters

Table 12.4.3.1 Metabolic abnormalities during treatment, worst grade per patient

	N	Grade 1		...	Grade 4		All*	
	N	N	%	...	N	%	N	%
Hyperglycemia	X	X	X.X		X	X.X	X	X.X
Hypoglycemia								
Hypoalbuminemia								
....								

(*) Any grade

Table 12.4.3.2 Metabolic abnormalities during treatment, worst grade per cycle

	N	Grade 1		...	Grade 4		All*	
	N	N	%	...	N	%	N	%
Hyperglycemia	X	X	X.X		X	X.X	X	X.X
Hypoglycemia								
Hypoalbuminemia								
....								

(*) Any grade

Listing 12.4.3.3 Grade 3-4 metabolic abnormalities during treatment. Worst grade by patient

Patient id.	Test	Grade

Listing 12.4.3.4 Grade 3-4 metabolic abnormalities during treatment. Worst grade by cycle

Patient id.	Cycle	Test	Grade

Listing 12.4.3.5 Metabolic tests not assessed at any treatment visit by patient

Patient id.	Lab. test

Listing 12.4.3.6 Metabolic tests not assessed by patient and cycle

Patient id.	Cycle	Lab. test

12.4.4 Laboratory values over time

In this section, grades 3-4 hematological and liver enzyme abnormalities will be displayed according to the cycle in which they occurred.

Table 12.4.4.1 Evolution of hematological abnormalities from baseline, worst case per patient.

			Worst grade per patient					Total	
			0	1	...				
Baseline	Neutropenia	Grade 0							
		Grade 1							
								
	Thrombocytopenia	Grade 0							
		Grade 1							
								
	Grade 0							
		Grade 1							
								

Table 12.4.4.2 Evolution of transaminases abnormalities from BL, worst case per patient.

			Worst grade per patient						Total	
			0		1		...		N	%
			N	%	N	%	N	%	N	%
Baseline	AST increase	X	X.X	X	X.X			X	X.X	
		Grade 1								
									
	ALT increase	Grade 0								
		Grade 1								
									
	Grade 0								
		Grade 1								
									

Table 12.4.4.3 Grade 3-4 laboratory abnormalities in the first cycle and in all other cycles

Laboratory abnormalities						
	Cycle 1			Cycle>1		
	No. of cycles evaluated	No. of cycles grade 3-4	%	No. of cycles evaluated	No. of cycles grade 3-4	%
Thrombocytopenia	X	X	X.X	X	X	X.X
Neutropenia						
ALP						
Total bilirubin						
AST						
ALT						
CPK						

Table 12.4.4.4 Hemtological time-course pattern

Laboratory abnormalities	Onset day grade 3-4	Days in grade 3-4	Day of recovery to grade 2			Days to recovery		
			<=28	29-35	>35	<=28	29-35	>35
Anemia	X (X-X)	X (X-X)	X (X.X%)	X (X.X%)	X (X.X%)	X (X.X%)	X (X.X%)	X (X.X%)
Neutropenia								
Thrombocytopenia								

Table 12.4.4.5 ALT/AST/CPK time-course pattern

Laboratory abnormalities	Onset day grade 3-4	Days in grade 3-4	Day of recovery to 2.5 x ULN			Days to recovery		
			<=28	29-35	>35	<=28	29-35	>35
ALT	X (X-X)	X (X-X)	X (X.X%)	X (X.X%)	X (X.X%)	X (X.X%)	X (X.X%)	X (X.X%)
AST								
CPK								

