#### Permitted windows for assessments

±1 day for study treatment administration and clinical assessments (ECOG PS, vital signs, weight, BSA, neurological assessment—always prior to infusion).

–2 days for hematology, biochemistry-A, serum  $\beta$ -2 microglobulin, biochemistry-B and coagulation tests. Note: windows for laboratory assessments only apply prior to the scheduled infusion, that is within 48 hours before the next scheduled infusion (except CID1).

- (1) EOT assessments should take place approximately 30 days ( $\pm$  one week) after discontinuation of study treatment or as soon as possible after the End of Cycle 6 radiological and clinical assessments (if the patient discontinues). Failure to attend the EOT visit exclusively due to a deteriorated clinical condition will not be considered a protocol deviation. The listed assessments are required if no recent data are available (i.e. within the previous 10 days) or if the last data available show a grade  $\geq$  2 treatment-related alteration whenever the medical condition of the patient allows.
- (2) The patient's anonymized local histopathology report must be provided as early as possible in the screening process for central pathological review. Cancer history includes: primary diagnosis; prognostic factors at first diagnosis (PIT, IPI, PIAI); prior treatment(s) with best response and TTP; documented relapse or refractory disease. Prognostic Index for Peripheral T-cell lymphoma (PIT) uses four variables as predictive for survival: age, PS, LDH level, and BM involvement (see [Appendix 3](#)). The standard International Prognostic Index (IPI) comprises the following variables: age  $\geq$  60 years, disease stages III to IV, LDH  $>$  normal, extranodal sites (ENSs)  $>$  one and PS  $\geq$  2. The alternative Prognostic Index for AITL (PIAI) comprises the following factors: age  $\geq$  60 years, PS  $\geq$  2, ENSs  $>$  one, B symptoms and platelet count  $<$   $150 \times 10^9/L$  (see [Appendix 4](#)). Ann-Arbor staging is also required (see [Appendix 5](#)).
- (3) Not necessary on CID1 if performed within the seven previous days and there is no change in the patient's clinical status and medications. To be performed at least every other day in the presence of grade 4 non-febrile neutropenia or febrile neutropenia, and every day in the presence of grade 4 thrombocytopenia until recovery.

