## 5.8 EVALUATIONS DURING TREATMENT

The assessments listed in [Table 5](#) below will be made while the patient is on treatment: see also [Figure 3. Study design](#).

**Table 5.** Evaluations during treatment.

	ASSESSMENT	TIME
1. Clinical examination	
 
◆ Complete physical examination, including weight and BSA.
 
◆ Basic neurological examination.
 
◆ Performance status (ECOG PS).
 
◆ Vital signs: heart rate, blood pressure and body temperature.
 
	By Day 1 of each cycle (always prior to plitidepsin administration).
	
 
◆ Concomitant therapies.
 
	Throughout the on-treatment period.
2. Laboratory tests	
 
◆ Hematology: differential WBC, hemoglobin, hematocrit and platelets.
 
	Cycle 1: Day 1, 8, 15 and 22 (always prior to plitidepsin administration). Not necessary on C1D1 if performed within the seven previous days and there is no change in the patient's clinical status and medications. To be performed at least every other day in the presence of grade 4 non-febrile neutropenia or febrile neutropenia, and every day in the presence of grade 4 thrombocytopenia until recovery. Cycle 2 and beyond: Day 1, 8 and 15 of each cycle (always prior to plitidepsin administration).
	
 
◆ Biochemistry-A: AST, ALT, total bilirubin (direct bilirubin if total bilirubin > 1.5 × ULN), ALP, creatinine, calculated creatinine clearance (Cockcroft-Gault formula), glucose, serum electrolytes (Na+, K+, Mg++, Ca++) and CPK (CPK-MB fraction should be measured if CPK is abnormally high).
 
	Cycle 1: Day 1, 8, 15 and 22 (always prior to plitidepsin administration). Not necessary on C1D1 if performed within the seven previous days and there is no change in the patient's clinical status and medications. To be performed at least every other day in the presence of grade 3/4 vomiting or any other drug-related SAE. Cycle 2 and beyond: Day 1, 8 and 15 of each cycle (always prior to plitidepsin administration).

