## 7.2 ADMINISTRATION OF STUDY MEDICATION

Plitidepsin will be administered intravenously as a 1-hour infusion (fixed rate) via central or peripheral venous catheter.

Patients will receive plitidepsin at a starting dose of 3.2 mg/m^2 on Day 1, 8 and 15 every four weeks (q4wk). A 1-day window is allowed for plitidepsin administration.

A cycle is defined as a four-week period.

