7.2 Clinical laboratory evaluation

Laboratory results will be classified according to the NCI-CTCAE version 4. All laboratory visits reported as “End of treatment” visit will be mapped to the last cycle visit.

For hematology values: absolute neutrophil count, lymphocyte count, WBC count, platelet count and hemoglobin worst grade per patient and per cycle will be displayed.

Time and duration of anemia, neutropenia and thrombocytopenia in cycles with grade 3-4 abnormality will be tabulated.

Overall cross tabulation will be presented for the worst grade during treatment versus the baseline toxicity grading of anemia, lymphopenia, leukopenia, neutropenia and thrombocytopenia.

The worst grade per patient during treatment and per cycle will be also calculated for the biochemical tests: ALT, AST, Total bilirubin, AP, CPK, creatinine, calcium, potassium, sodium, glucose and albumin.

Time and duration of AST, ALT and CPK increases in cycles with grade 3-4 abnormality will be tabulated.

Overall cross tabulation will be presented for the worst grade during treatment versus the baseline toxicity grading of AST, ALT and CPK increase.

7.3 Vital signs, physical examination, left ventricular ejection fraction (LVEF) and electrocardiogram findings

Tabulation will be made summarizing the performance status, body weight, LVEF and electrocardiogram abnormalities at baseline and during the treatment for each patient.

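### Cycle 1 has a scheduled Day 22 blood draw and later cycles do not, so the SAP's by-cycle laboratory displays can show a fall in grade 3-4 toxicity, or mask a rise, through sampling alone

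*SAP*

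**What the plan says.** **Sampling.** Protocol Section 5.8, Table 5, gives the same pattern for hematology and for Biochemistry-A. For the first cycle it reads "Cycle 1: Day 1, 8, 15 and 22 (always prior to plitidepsin administration"; for the rest, "Cycle 2 and beyond: Day 1, 8 and 15 of each cycle (always prior to plitidepsin administration". The grid in the Schedule of Assessments and Procedures agrees: Day 22 is marked for these panels in Cycle 1 and blank in further cycles. The schedule's notes add that "windows for laboratory assessments only apply prior to the scheduled infusion, that is within 48 hours before the next scheduled infusion", with an exception for Cycle 1 Day 1. Protocol Section 7.2 gives plitidepsin "on Day 1, 8 and 15 every four weeks (q4wk", a cycle being four weeks.

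**Analysis.** SAP Section 12.4.4 includes "Table 12.4.4.3 Grade 3-4 laboratory abnormalities in the first cycle and in all other cycles". For platelets, neutrophils, ALP, bilirubin, AST, ALT and CPK it sets the percentage of evaluated cycles with grade 3-4 in Cycle 1 beside that in Cycle >1. Section 12.4.1 says "These tables will be complemented with plots for the median nadir of neutrophils (Figure 12.4.1.8), platelets count (Figure 12.4.1.9"), then adds hemoglobin, all by cycle. Section 12.4.2 does the same for the median peak of ALT, AST and CPK. Section 12.4.1 also says that "graphs comparing the time course during the first and second cycle will be created". Under Section 7.2, each laboratory visit recorded as End of treatment "visit will be mapped to the last cycle visit".

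The SAP does not restrict these comparisons to draw days shared by all cycles, and it carries no footnote on the unequal schedule. It does not say to which cycle a pre-dose Day 1, unscheduled or End of Cycle 6 value belongs.

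**The concern.** A percentage of cycles with any grade 3-4 value, or a median worst value per cycle, depends on how often and when blood is drawn. Cycle 1 has a look at the week after the third dose; later cycles have no scheduled look there. Comparing the two mixes toxicity with opportunity to detect it.

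The trial has a single arm, so no control group on the same schedule would expose the artefact. A lower percentage and shallower nadirs after Cycle 1 could be taken as absence of cumulative toxicity, or as dose reductions working, when some of the difference comes from the missing Day 22 sample. Equally, a real rise in later cycles could be flattened.

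**Working it through.** The documents state no rate, power or expected value for this comparison, so there is no planned figure to reproduce. The check has two parts: set the draw days side by side, then see what unequal draws do when true toxicity is equal.

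**1. Draw days** (Protocol Table 5, the assessment schedule and its windows, Section 7.2)

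| Draw | Cycle 1 | Cycle 2 onward |
|---|---|---|
| Day 1, pre-dose | before any exposure | after earlier cycles |
| Day 8, pre-dose | yes | yes |
| Day 15, pre-dose | yes | yes |
| Day 22 | yes | none |
| Next Day 1 (Day 29), up to 48 h early | Day 27-29 | Day 27-29 |

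Within the cycle there are three post-dose draws in Cycle 1 (Days 8, 15, 22) and two later (Days 8, 15). In later cycles nothing is scheduled between the Day 15 dose and the next pre-dose draw, nominally 14 days on.

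**2. Equal true risk, independent draws.** Let p be the assumed chance of grade 3-4 at each post-dose draw. A cycle counts as affected with probability 1-(1-p)^k, where k = 3 in Cycle 1 and k = 2 later. Later Day 1 draws are taken as never grade 3-4.

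| p | Cycle 1 | Later | Relative fall |
|---|---|---|---|
| 0.02 | 1-0.98^3 = 5.9% | 1-0.98^2 = 4.0% | 32.7% |
| 0.05 | 1-0.95^3 = 14.3% | 1-0.95^2 = 9.8% | 31.6% |
| 0.10 | 1-0.90^3 = 27.1% | 1-0.90^2 = 19.0% | 29.9% |
| 0.15 | 1-0.85^3 = 38.6% | 1-0.85^2 = 27.8% | 28.1% |

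**3. Later Day 1 draws counted in their own cycle,** with chance q of grade 3-4: the later rate is 1-(1-p)^2(1-q). With q = p/2, p = 0.05 gives 1-0.9025×0.975 = 12.0% (fall 15.8%) and p = 0.10 gives 1-0.81×0.95 = 23.1% (fall 14.9%). With q = p the fall is 0.

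**4. Correlated draws.** Take 12% as an assumed Cycle 1 rate. It is borrowed from the grade 3/4 neutropenia figure for the earlier PTCL cohort in Protocol Section 1.3, which is not a first-cycle rate. Three draws with first-order serial correlation rho were simulated 1,000,000 times, and the same grade 3-4 threshold was then applied to the first two only.

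| rho | Later rate | Median nadir looks better by |
|---|---|---|
| 0 | 8.2% | 0.27 SD |
| 0.5 | 8.6% | 0.24 SD |
| 0.8 | 9.4% | 0.17 SD |
| 0.95 | 10.5% | 0.09 SD |

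**5. Without a model.** If a share f of affected first cycles is detected only on Day 22, the later rate at equal toxicity is the Cycle 1 rate times (1-f). From 12%, f = 10% gives 10.8%, f = one third gives 8.0%, and f = 0 gives 12.0%, that is, no artefact.

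**6. Common days only.** With Days 8 and 15 in both columns, equal toxicity gives equal rates: at p = 0.05, 9.8% against 9.8%.

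**The case against.** **Day 1.** Only Cycle 1 Day 1 precedes exposure. If each later Day 1 draw counts in its own cycle at equal risk, the fall disappears (step 3). If it counts as the close of the preceding cycle at equal risk, the comparison is four draws against three: 18.5% v 14.3% at p = 0.05 and 34.4% v 27.1% at p = 0.10, ratios 1.30 and 1.27. The arithmetic is right, but equal risk is hard to sustain. Under Protocol Section 7.4, a draw that releases a new cycle must show bilirubin and AST/ALT at grade 1 or below and muscular toxicity, including CPK, below grade 2. That rules out grade 3-4 in four of the seven rows. The neutrophil and platelet floors should generally do the same for two more. That is an assumption, because the documents do not reproduce the CTCAE count limits and the synopsis allows baseline neutrophil values with extensive marrow infiltration. ALP has no limit of its own there. Draws that fail and delay a cycle could offset the gap, but the SAP does not say where they count.

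**Other offsets.** End-of-treatment values mapped to the last cycle add a draw to Cycle >1 for anyone who goes beyond Cycle 1, which works against a fall. Extra draws triggered by grade 4 or febrile neutropenia, or by grade 4 thrombocytopenia, apply in any cycle, but they begin only once the abnormality is known and so do not replace a missed first detection.

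**Reach.** A reader might infer that the displays will show a fall. The documents do not support that: they do not say when the nadir or peak occurs or how strongly weekly draws correlate. A reader might also extend the point to Tables 12.4.4.4 and 12.4.4.5. These are not split by cycle and cannot show a fall; the late-cycle gap only coarsens duration and recovery day. The first-versus-second-cycle graphs plot a time course, where a missing Day 22 point should be visible.

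**Weight.** These are descriptive outputs with no test or decision rule, and later cycles are already a selected, dose-modified group. That stands, and it limits the importance of the point. It does not justify adding an avoidable sampling difference.

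**Conclusion.** The sampling difference is certain from the documents, and the SAP does not allow for it. Table 12.4.4.3 and the by-cycle nadir and peak plots can therefore show an apparent fall after Cycle 1, or mask a true rise. The extra Cycle 1 draw pushes in that direction; whether a net fall appears, and how large it is, cannot be derived from the documents.

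The 14.3-27.1% against 9.8-19.0% rests on equal true risk, independent draws, an assumed 5-10% per draw, and later Day 1 values never being grade 3-4. It is an illustration towards the upper end. Correlation brings 12% against 8.2% down to 12% against 10.5% over the range tried, and the gap is zero if Day 22 never provides the only detection. The consequence is confined to interpreting the safety profile over cycles; the primary ORR analysis is untouched.

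**What to change.** 1. Base the Cycle 1 versus Cycle >1 comparison in Table 12.4.4.3, and the by-cycle nadir and peak plots, on the scheduled Day 8 and Day 15 values. Day 1 should stay out, because it is pre-exposure in Cycle 1 and post-exposure later.
2. Show Cycle 1 Day 22 in a separate row.
3. Give the all-values version alongside, unscheduled draws included, with a footnote that Day 22 is scheduled in Cycle 1 only.
4. State which cycle pre-dose Day 1, unscheduled, End of Cycle 6 and EOT values belong to, and keep EOT values mapped to the last cycle out of the common-day comparison.
5. Footnote Tables 12.4.4.4 and 12.4.4.5: later cycles have no scheduled draw between Day 15 and the next pre-dose draw. Nothing more is needed there.

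The cost is SAP wording and a filter in the table and figure programs; no new samples are needed. The common-day comparison uses fewer values and can understate absolute nadirs, so the worst-grade-per-patient tables should keep every value. It removes the schedule effect only; selection and dose modification after Cycle 1 remain.

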## 4. SELECTION OF PATIENTS

### 4.1 INCLUSION CRITERIA

- 1) Voluntary written informed consent of the patient (both to participate in the study and to provide biopsy samples) obtained before any study-specific procedure.
- 2) Age  $\geq 18$  years.
- 3) ECOG PS  $\leq 2$ .
- 4) Life expectancy  $\geq 3$  months.
- 5) Histologically confirmed diagnosis of R/R AITL (eligibility needs to be confirmed by central pathological review.\*)
- 6) At least a two-week washout period since the end of the last therapy (six weeks for a prior nitrosourea-containing regimen), recovery to grade  $\leq 1$  from any non-hematological AE derived from previous treatment (excluding alopecia).
- 7) Adequate BM, renal, hepatic, and metabolic function (assessed  $\leq 14$  days before inclusion in the study):
  - a) Absolute neutrophil count (ANC)  $\geq 1.0 \times 10^9/L$ .
    - Screening of ANC should be independent of granulocyte-colony stimulating factor (G-CSF) support for at least one week and of pegylated G-CSF for at least two weeks.
  - b) Platelet count  $\geq 75 \times 10^9/L$ .
  - c) Hemoglobin  $\geq 9$  g/dL.
    - Patients may receive red blood cells (RBC) and/or erythropoietin (EPO), and/or platelet transfusions in accordance with institutional guidelines.
  - d) Aspartate aminotransferase (AST) and alanine aminotransferase (ALT)  $\leq 3.0 \times$  the upper limit of normal (ULN).
  - e) Total bilirubin  $\leq 1.5 \times$  ULN.
  - f) Alkaline phosphatase (ALP)  $\leq 3.0 \times$  ULN ( $< 5 \times$  ULN, if isolated ALP increase, i.e., without ALT/AST or bilirubin increase).
  - g) Calculated creatinine clearance (CrCL)  $\geq 30$  mL/minute (Cockcroft-Gault formula).
  - h) Creatine phosphokinase (CPK)  $\leq 2.5 \times$  ULN.
  - i) Albumin  $\geq 2.5$  g/dL.
  - j) Normal value of electrolytes, including potassium, magnesium and calcium.
- 8) Left ventricular ejection fraction (LVEF) by echocardiogram (ECHO) or multiple-gated acquisition (MUGA) scan within normal range (according to institutional standards).

\* Patient inclusion can be approved based on local histopathological report(s). Eligibility will be confirmed using diagnosis and/or relapse biopsy specimens submitted for central pathological review prior to each futility analysis/end of study.

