## 7.4 CRITERIA FOR TREATMENT CONTINUATION

Patients can receive plitidepsin infusions (Day 1, 8, 15 of each cycle) for a maximum of six cycles (unless with PR or SD after Cycle 6: see Section [5.2.1.2](#)) if they fulfill the following requirements:

- ANC  $\geq 1.0 \times 10^9/L$ .
- Platelet count  $\geq 75 \times 10^9/L$ .
- Hemoglobin  $\geq 9.0$  g/dL.
- Calculated CrCL  $\geq 30$  mL/min (Cockcroft-Gault formula).
- Total bilirubin  $\leq 1.5 \times$  ULN ( $\leq$  grade 1).
- AST, ALT  $\leq 3.0 \times$  ULN ( $\leq$  grade 1).
- Normal value of electrolytes, including potassium, magnesium and calcium.
- Muscular toxicity (myalgia, muscular weakness, CPK increase)  $<$  grade 2.
- Other non-hematological drug-related AEs [except for increased gamma glutamyltransferase (GGT), not optimally treated nausea and vomiting, hypertension or alopecia]  $\leq$  grade 1.
- No clinically relevant ECG changes compared with grade at baseline.
- QTc must be  $\leq$  grade 1 before receiving the study treatment. In case of grade 1 QTc prolongation during treatment, and after discussion with the Sponsor, treatment must be continued with a normal value of electrolytes, including potassium, magnesium and calcium, being mandatory before the re-administration of plitidepsin.

- In case of QTc  $\geq$  grade 2, the study treatment must be discontinued, and the patient must be followed until recovery.

If these criteria are not met on Day 1 of any cycle after Cycle 1, the new cycle is to be delayed for up to two weeks until recovery. If these toxicities do not recover after a 2-week delay, the patient is to discontinue treatment and start the follow-up period unless there is obvious clinical benefit, in which case the patient might restart treatment at the Investigator’s discretion and after obtaining the approval of the Sponsor.

If these criteria are not met on Day 8 and 15 of any cycle (including Cycle 1), the scheduled infusion is to be omitted. Omitted doses for a given cycle are not to be recovered.

“Cycle delay”, therefore, is only applicable to the first infusion of a new cycle (i.e., Day 1) and not when an infusion takes place within the protocol-permitted window (one day) and not when treatment resumes after radiological assessment (see Section 5.10).

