## **8.2 SAFETY**

Patients will be evaluable for safety if they have received any partial or complete treatment cycle. All AEs will be graded according to the NCI-CTCAE, v.4 and will be coded using the Medical Dictionary for Regulatory Activities (MedDRA). Cycle delays, skipped doses, dose reduction requirements, and reasons for treatment discontinuation will be monitored throughout the study.

The safety profile of patients will be monitored throughout the treatment and up to 30 days after the last treatment dose (EOT), or until the patient starts a new antitumor therapy or until the date of death, whichever occurs first.

Any treatment-related AEs will be followed until recovery to at least grade 1 or stabilization of symptoms, whenever possible.

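### SAP Table 12.4.4.5 measures ALT/AST recovery against 2.5 x ULN, which is the protocol's CPK limit and not its ALT/AST limit of 3.0 x ULN

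*SAP*

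**What the plan says.** SAP Appendix I, section 12.4.4, Table 12.4.4.5 has one row each for ALT, AST and CPK under a single header, "Day of recovery to 2.5 x ULN", with bins of up to 28, 29 to 35 and over 35 days. A second block with the same bins, *Days to recovery*, has no stated starting day. The SAP text behind the table is in section 7.2: "Time and duration of AST, ALT and CPK increases in cycles with grade 3-4 abnormality will be tabulated". The same section says: "Laboratory results will be classified according to the NCI-CTCAE version 4".

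For AST and ALT the protocol uses a different multiple. Section 4.1, item 7d, admits patients up to 3.0 x ULN. Section 7.4 repeats that limit as a condition for infusions and attaches a grade to it: "AST, ALT $\leq 3.0 \times$ ULN ( $\leq$ grade 1"). Section 8.2 sets the follow-up target: "Any treatment-related AEs will be followed until recovery to at least grade 1 or stabilization of symptoms, whenever possible".

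In the protocol, 2.5 x ULN appears only for CPK: as the entry limit in section 4.1, item 7h, and in the exclusion for persistent CPK elevation in section 4.2, item 2j. Neither document says why the SAP applies it to transaminases.

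**The concern.** The table reports when a laboratory value has recovered. For ALT and AST its line is stricter than the value the protocol calls grade 1, accepts at entry and accepts for further infusions. The simplest reading is that a CPK limit was carried across a shared header.

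Two consequences follow. A patient whose ALT or AST lies above 2.5 and at or below 3.0 x ULN is unrecovered in this table while meeting the protocol's grade 1 boundary. And a patient who entered the trial in that range, had a grade 3-4 rise and came back exactly to baseline is also unrecovered, because the SAP has no rule for a baseline above the cut-off. At stake is how slow liver-enzyme recovery looks in the safety report. The primary endpoint, the sample size, the error rates and the dosing rules do not depend on this table.

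**Working it through.** The plan gives no figure to reproduce here, so the check compares thresholds and then gauges the possible size.

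**1. Thresholds side by side**

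| Analyte | Protocol entry (4.1) | Protocol continuation (7.4) | SAP Table 12.4.4.5 |
|---|---|---|---|
| ALT, AST | 3.0 x ULN | 3.0 x ULN, labelled grade 1 or lower | 2.5 x ULN |
| CPK | 2.5 x ULN | below grade 2 | 2.5 x ULN |

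**2. Direction.** Any value at or below 2.5 is also at or below 3.0. The first day at or below 2.5 therefore cannot precede the first day at or below 3.0. This needs no assumption.

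**3. Size in continuous time.** Assume first-order decline with half-life h from peak P to baseline b, all in multiples of ULN. The time to threshold c is t = (h / ln 2) x ln[(P - b) / (c - b)]. Here h, P and b are assumptions; the documents give none.

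- Decline toward zero: the gap is h x ln(3.0/2.5) / ln 2 = 0.263 h. For h of 1, 3, 7 and 14 days this is 0.3, 0.8, 1.8 and 3.7 days.
- P = 8, with time to 3.0 against time to 2.5:

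| Baseline | h = 3 days | h = 7 days |
|---|---|---|
| 1.0 | 5.4 vs 6.7 | 12.7 vs 15.6 |
| 2.4 | 9.7 vs 17.4 | 22.6 vs 40.7 |
| 2.6 | 11.3 vs not reached | 26.3 vs not reached |
| 2.8 | 14.1 vs not reached | 32.9 vs not reached |

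The gap widens as baseline nears 2.5. Above 2.5, return to baseline alone does not meet the SAP cut-off.

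**4. Size on the scheduled visits.** Protocol section 5.8, Table 5, schedules biochemistry-A on Days 1, 8, 15 and 22 of Cycle 1 and on Days 1, 8 and 15 thereafter; Day 29 is Day 1 of the next cycle. Take peaks of 6, 8 and 12 x ULN on Day 8 or 15, half-lives of 3, 5 and 7 days, baseline 1.0, and both visit schedules: 3 x 2 x 3 x 2 = 36 scenarios. Assume that cycles start on time and that re-exposure does not change the decline.

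One example: peak 6 on Day 8 with h = 5 reaches 3.0 on day 8 + (5 / ln 2) x ln(5/2) = 14.6, and 2.5 on day 8 + (5 / ln 2) x ln(5/1.5) = 16.7. In Cycle 1 the recorded day moves from 15 to 22. In later cycles it moves from 15 to 29.

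Over all 36:

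- The recorded day is the same in 27 and later in 9 (by 7 days in eight, by 14 days in one).
- The day-of-recovery bin is unchanged in 28 and later in 8. The ninth shift, from day 15 to day 22, stays within the first bin.
- If *Days to recovery* is counted from the peak day, no bin changes. The longest such interval is 36 - 15 = 21 days, or 29 - 8 = 21 days.

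**5. A boundary case.** Suppose ALT first falls to 2.7 x ULN on Day 29. At a 3.0 cut-off, recovery is in the 29-35 bin. At 2.5, the next scheduled sample is Day 8 of the new cycle, day 36 from the old cycle's start, so recovery is over 35 days at the earliest and is read after another infusion. Unscheduled samples would narrow this.

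**The case against.** The strongest reply is that the header says exactly what it reports. Time to 2.5 x ULN is not wrong as time to 2.5 x ULN; it is late only against a line the table does not claim to use. The companion hematology table, 12.4.4.4, takes recovery to grade 2, which is not the protocol's follow-up target either, so these columns need not restate protocol rules. Nor is information lost: Table 12.4.4.2 gives shifts from baseline and Listing 13.1.13 gives the values.

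Much of this stands. A reader might infer that the table is meant to show how long liver enzymes hold up re-treatment. The 28- and 35-day bins suggest it, but neither document says so, and SAP sections 12.1.2 and 12.1.3 report delays and omissions separately. A reader might also infer that every recovery time is overstated, or every episode passing through 2.5 to 3.0 x ULN affected. Step 4 shows otherwise: most recorded days and bins do not move.

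What does not stand is that the cut-off is therefore only a matter of taste. The protocol assigns a grade to 3.0 x ULN for these two enzymes, and the SAP grades laboratory results. Calling a value the protocol labels grade 1 unrecovered needs a reason, and none is given.

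**Conclusion.** The mismatch is real and minor. For ALT and AST, Table 12.4.4.5 can show recovery later than the protocol's grade 1 boundary would, and never earlier. A patient enrolled above 2.5 and up to 3.0 x ULN who only returns to baseline is shown as not recovered.

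The stronger reading, that such a patient can never recover, is not supported: the patient is counted once the enzyme falls to 2.5 x ULN or lower. Such a patient also enters the table only after a grade 3-4 rise, and the documents do not show how many, if any, there will be.

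The direction and the baseline problem follow from the documents alone. The counts of 9 and 8 out of 36 rest on the assumed peaks, half-lives, baseline and on-time visits; they illustrate what can happen and do not estimate a rate. The CPK row matches the protocol's entry limit and is not in question.

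**What to change.** In Table 12.4.4.5, make the recovery column analyte-specific: at or below 3.0 x ULN for ALT and AST, and 2.5 x ULN for CPK as now. Add a footnote that return to baseline counts as recovery when baseline exceeds the cut-off. The same footnote could state the day from which *Days to recovery* is counted, since the bins depend on it.

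This changes tabulation only and takes no position on the entry or continuation limits. The cost is one header and one footnote, best settled before the table is programmed. The downside is that ALT/AST recovery is no longer shown on the stricter cut-off, although it can still be derived from the listed biochemistry values.
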